## **15.6.2.** Sponsor records

Medtronic will keep, among others, the following records:

[figure not shown]
- All correspondence (including the correspondence with the authorities and the EC, if necessary) relating to the investigation, including the EC authorization letter
- Signed clinical trial agreement
- All serious adverse events
- All of the site's specific forms for subject informed consents
- Clinical Investigation Plan and amendments
- Name of the main investigators and the sites where the clinical research will be performed
- Approval of the study documents
- Electronic CRF

#### 15.7. Publication and use of the information

The Publication Plan, separate document from this Protocol, describes the procedures for the development of publications, criteria for determining authorship, prioritization of proposals, and Version 1.0 RECABA

procedures for developing, revising, and approving abstracts, manuscripts, and public presentations. The Publication Plan internally approved by the Scientific Committee and Medtronic will be used as a guide for publications process.

The transparency of the study results will be maintained in the following manner: By registering the study on ClinTrials.gov, recording and communicating the results on ClinicalTrials.gov; by presenting the publication of the results of the objectives defined in the protocol after its conclusion and the results of the complementary proposals throughout the study; by divulging the financial interests of the authors of the publication according to the policies established by the corresponding journals and conferences; and by making the study data of each site accessible to the corresponding investigator after the trial has ended.

#### 15.8. Early termination or suspension

#### **15.8.1.** Early termination or study suspension

The Sponsor or the regulating authority may decide to suspend or terminate the study prematurely (for example if information comes to light indicating that the risk for subjects participating in the study is greater than was indicated initially, or if the intermediate analysis indicates that the results differ significantly from the objectives or statistical evaluation criteria of the study). If the study is terminated prematurely or suspended, the Sponsor will inform the clinical investigators of the termination or suspension of the study and the reasons for this decision. The evaluating ECs and the subjects in the study or their legal representatives must be informed.

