# 5. Study objectives and endpoints

## 5.1. Objectives

#### **5.1.1.** Primary Objective

To evaluate the efficacy of the cryoablation procedure at 12 months, defined as the absence of recurrences of atrial fibrillation.

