## 5.2. Endpoints

## **5.2.1.** Primary endpoint

The primary and secondary endpoints coincide with the primary and secondary objectives defined in section 6.1.

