#### 10. Risks and benefits

#### 10.1. Potential risks

Because it is an observational study of marketed products, there are no additional risks through participating in the study.

In the study, the products will be used in accordance with their labeling, therefore no risks different from those normally associated with standard clinical practice of the device are foreseen.

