# 13. Statistical design and methods

The following statistical analysis plan of the data will be carried out:

The variables analyzed will be those collected in the subject registry corresponding to the different protocols of the procedure, intervention data, complications, follow-up and long-term results in these subjects. In the Method section there is a list of variables of interest.

Recurrence of AF will be defined as a clinically diagnosed episode of AF and accordingly documented (on ECG, Holter monitor with a duration of at least 30 seconds or implantable devices or event recording systems).

It is expected to carry out 3 analyses of the primary and secondary objectives described in the Clinical Investigation Plan:

- 1. At the end of the first year of enrollment
- 2. At the end of the second year of enrollment
- 3. At the end of follow-up

On the other hand, there will be 4 analyses of additional proposals throughout the study (see Appendix B: Publications Plan)

- Two analyses at the end of enrollment.
- Two analyses at the end of follow-up.

Each of the variables of interest will be described univariantly and individually.

Crosses of variables will also be carried out to describe each one of the clinical strata of interest.

When it is possible and of interest for the investigators, statistical comparisons between strata will be carried out through statistical tests.

Specific statistical models to respond to the interests of the investigators will be proposed, such as comparison of the procedures or comparison of subject strata.

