## 13.1. Analysis of clinical data

It is expected to include approximately 1000 subjects enrolled at approximately 30 Spanish sites, with an enrollment period of 2 years and a follow-up period of one year from the time of enrollment of each subject. The subjects analyzed will be the ones included in the RECABA study database: "Spanish Registry of Cryoballoon Ablation". The variables analyzed will be those mentioned previously with the intention of adequately describing the activity of the clinical sites, the procedures used and the diseases treated in accordance with standard clinical practice.

All the data are anonymized in origin so that it is not possible to identify the subjects.

The collection of data will be prospective from the time of enrollment.

The database will be received codified and debugged, and the allocation of the lost values that have been decided previously.

The basic report at the end of enrollment and at the end of the follow-up period will consist of: The quantitative variables are expressed as mean, median, typical deviation and interquartile range depending on which is most suitable for the distribution of values. The differences between groups in relation to the quantitative variables will be evaluated through the student t test for independent samples or the analysis of variance (depending on the number of groups compared) and between variables through the student t test for related samples or the analysis of variance of repeated measures, as applicable. To analyze the relationships between categorical variables the chi-squared test ( $\chi^2$ ) and the Fisher's exact test will be used. The differences of proportions will be assessed through the homogeneity test  $\chi^2$ . To assess the relationships between the quantitative variables the Pearson or Spearman r correlation will be used, as appropriate.

The intermediate statistical reports proposed by the investigators will depend on the hypotheses suggested by the investigator. They will include at least a descriptive analysis such as the one described previously. In addition, the appropriate models to respond to the hypotheses proposed will be estimated, which can include techniques of the style of exploratory factor analysis, analysis of multiple contingency, analysis of logistical regression, analysis of conglomerates or analysis of multifactorial variance.

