A nominal significance of a=0.05 will be assumed for a result to be considered statistically significant. The statistical analysis will be achieved using the statistical packet SPSS 20.0.

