### **Statistical models**

In order to conclude on the primary objective of the study, the number and percentage of cases with absence of atrial fibrillation recurrences will be calculated after 12 months of follow-up, after the cryoablation procedure. The scientific coordinators of the study will have to determine the closing date of the database so that it has been possible to collect information from 12 months of follow-up of a sufficiently large number of patients.

The protocol defines AF recurrence as a clinically diagnosed and documented episode of AF (using ECG, Holter monitor with a duration of at least 30 seconds, or using implantable devices

or event monitoring systems). The information necessary to determine the existence of a recurrence of AF will be extracted from the Follow-up and Adverse Events tables.

The existence of differences between patients with and without recurrence in clinical variables and patient follow-up will be explored. Student's t statistics (for continuous variables) and  $\chi^2$  (for categorical variables) will be used. If there are appreciable differences between the groups of patients in the clinical variables, logistic regression models will be proposed to study the multivariate effect of the variables and assess their predictive capacity.

The waiting times until the moment of recurrence of AF will be described using survival models (survival tables and Kaplan-Meier) and the existence of variables capable of predicting the differences between both groups of patients will be explored.

The necessary statistical analyzes will be approached to verify the secondary objectives based on the variables designated by the study coordinators.

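### The protocol allows termination on interim results with no criterion to judge them by, and does not require 12-month data collection to be completed after a stop

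*Protocol*

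**What the plan says.** Protocol section 15.8.1 lets the sponsor or the regulating authority suspend or end the study early. It gives two examples. One is new information that risk is greater than first indicated. The other is the case "if the intermediate analysis indicates that the results differ significantly from the objectives or statistical evaluation criteria of the study".

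The places where such a criterion could stand are these:

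- Protocol 5.1.1, primary objective: "To evaluate the efficacy of the cryoablation procedure at 12 months, defined as the absence of recurrences of atrial fibrillation". No target rate is given.
- Protocol 5.2.1: "The primary and secondary endpoints coincide with the primary and secondary objectives". Nothing is added.
- Protocol 8.1: about 1000 subjects, a number based on the yearly volume of procedures in Spain.
- Protocol 13: "It is expected to carry out 3 analyses of the primary and secondary objectives described in the Clinical Investigation Plan", at the end of the first and second enrolment years and at the end of follow-up.
- Protocol 13.1: "A nominal significance of a=0.05 will be assumed for a result to be considered statistically significant". There is no null value, boundary or adjustment for repeated looks.
- SAP, Statistical models: "the number and percentage of cases with absence of atrial fibrillation recurrences will be calculated after 12 months of follow-up". There is no threshold, and the SAP has no section on interim analysis or stopping.

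After a stop, sections 15.8.1, 15.8.2 and 15.9 require that the parties concerned be informed. They do not say whether data on subjects already ablated are still collected. The SAP section on missing values assigns a subject with no information at database close the status last validly recorded. The SAP section on statistical models leaves the closing date to the scientific coordinators.

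**The concern.** The results-based example needs something for the results to differ from, and the documents supply nothing. Three looks at the primary objective are scheduled, so interim results will be available. Whoever invoked the example would have to choose the reference value, and the meaning of a significant difference, with those results in hand.

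Two consequences are possible. The first is selection: a study that stops because its interim percentage looks extreme reports that extreme percentage. The second is truncation: if data collection ends with the study, subjects ablated in the preceding year never reach 12 months, and AF-related events after day 30, which section 11.2 collects throughout the study, are cut off as well. The working below shows that the second is the larger problem.

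**Working it through.** The plan has no figure to reproduce here: 1000 is a volume-based number, with no power, margin or precision target behind it.

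**Inputs from the documents.** 1000 subjects; 24 months of enrolment; 12 months of follow-up (visit window 28 days either way); 3-month blanking period; looks at months 12, 24 and 36.

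**Assumptions, not in the documents.** Even accrual; true 12-month freedom from recurrence of 70% (range 70% to 80%); constant recurrence hazard after blanking, none counted before; recurrences known up to the stop date; for the selection step only, a two-sided z-test at 0.05 against an assumed target at month 24.

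**1. Who has 12 months of follow-up at each look.** The number is 1000 × (T − 12)/24.

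- Month 12: 500 enrolled, 0 complete (about 38 if the early edge of the window counts: 1000 × (28/30.44)/24).
- Month 24: 1000 enrolled, 1000 × 12/24 = 500 complete (about 538 with the window).
- Month 36: all 1000 complete.

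**2. Precision.** The half-width is 1.96 × √(p(1 − p)/n), with p = 0.70.

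- n = 1000: 1.96 × √(0.21/1000) = 2.84 points.
- n = 500: 1.96 × √(0.21/500) = 4.02 points.

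**3. Selection bias from the stop.**

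- Truth equal to target (70%): a stop occurs about 5% of the time. The standard error at n = 500 is √(0.21/500) = 2.05 points. The mean of |Z| given |Z| > 1.96 is 2 × 0.0584/0.05 = 2.34. The mean absolute deviation given a stop is 2.34 × 2.05 = 4.8 points. The deviations fall on both sides, and an ordinary estimate from 500 subjects already misses by 0.80 × 2.05 = 1.6 points on average.
- Truth 5 points from target (simulated, truth 70% to 80%): the chance of a stop is 0.68 to 0.78. Stopped estimates are off by 0.7 to 1.0 point, away from the target. A stopped study loses the second 500 subjects, which would have halved that error, so the overall bias is P(stop) × half the error. For truth 70% and target 75% this is 0.736 × 0.5 × 0.91 = 0.33 point. Across the four pairs simulated it is about 0.3 point.

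**4. Truncation with last status carried forward.** Let S be the true 12-month freedom. The hazard after month 3 is h = −ln(S)/9. Subjects still in follow-up at the stop have elapsed times spread evenly over 0 to 12 months, so their average freedom is A = [3 + (1 − S)/h]/12.

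For S = 0.70: h = 0.3567/9 = 0.0396; (1 − S)/h = 0.30/0.0396 = 7.57; A = 10.57/12 = 0.881.

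- Month-12 stop: everyone is still in follow-up, so the crude percentage is A.
- Month-24 stop: half are complete, so it is (S + A)/2 = (0.70 + 0.881)/2 = 0.790.

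| True 12-month freedom | Month-24 stop | Month-12 stop |
|---|---|---|
| 70% | 79% | 88% |
| 75% | 83% | 90% |
| 80% | 86% | 92% |

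The upward error is about 6 to 9 points for a month-24 stop and 12 to 18 points for a month-12 stop. If the percentage were instead limited to subjects with a full 12 months, this error would not arise. A month-24 stop would then leave 500 subjects, as in step 2, and a month-12 stop almost none.

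**The case against.** The strongest reply is that this is a descriptive, non-interventional registry, and that the clause is one illustrative example which nothing suggests anyone expected to use. Section 13 does not designate its three analyses as stopping analyses. That is fair, and it limits the weight of the point. It does not supply the missing criterion.

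Several stronger readings are tempting, and the documents do not support them:

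- **That the sponsor alone decides.** Section 15.8.1 also names the regulating authority. Section 12 lists only a Publications Committee, but a Scientific Committee exists: it takes part in extending follow-up (6.1), is consulted on doubtful event classification (11.2) and must agree amendments (15.5). It has no stated role in stopping.
- **That a stop could pass unexplained.** Reasons go to the investigators, and ethics committees and subjects must be informed (15.8.1). Closeout is justified to investigators, ethics committees and the Scientific Committee (15.9), and results are to be registered and published (15.7). These constrain a results-driven stop, but do not require follow-up to be completed.
- **That termination necessarily ends follow-up.** The text is silent. The silence applies equally to a stop for risk or by order of an authority.
- **That a results-based stop could protect nobody.** Section 10.1 says "there are no additional risks through participating in the study", which concerns the added risk of taking part. It does not address whether a pause could serve a review of the device. New risk has its own ground in 15.8.1.
- **That all information on incompletely followed subjects is lost.** The SAP also plans survival tables and Kaplan-Meier, where these subjects contribute about 6 months each on average under even accrual. With censoring, that analysis would limit the bias. However, the SAP answers the primary objective with the crude percentage.
- **That a half-width of 4.0 points breaches a precision target.** None was set.

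**Conclusion.** The point holds in a limited form. The objectives exist, but no target value, hypothesis or boundary does, so the results-based example in 15.8.1 cannot be applied without choosing a reference after the fact. Nothing in 15.8 or 15.9 secures the 12-month data of subjects already ablated.

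A reader might infer that a stop would bias the answer by nearly 5 points. That figure is a mean absolute deviation, given a stop that happens about 5% of the time when truth equals target. Where a stop is likely, because the truth is 5 points off, the average bias is about 0.3 point.

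Truncation is the main harm. It removes the 12-month outcome for about half the cohort at month 24 and nearly all of it at month 12. Under the carry-forward rule it raises the crude percentage by 6 to 9 or 12 to 18 points respectively, which favours the device. These sizes rest on the assumptions listed above, and on the carry-forward rule being applied to the primary percentage. The harm is possible rather than certain, since it needs both a stop and an end to data collection. The change should be made because it costs little.

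**What to change.** In section 15.8.1, replace the interim-result example with a statement that interim AF-recurrence results are not a ground for termination. Deleting the example alone would not be enough, because the list is illustrative and the general discretion would remain. Keep the new-risk ground and the authority's powers as they are.

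Add to the same section: if enrolment stops for any reason, subjects already ablated complete the routine 12-month data collection, unless they withdraw or an authority requires otherwise, and all their results are reported.

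In the SAP, state that follow-up left unobserved after a stop is censored, not carried forward, and that the 12-month result is then taken from the Kaplan-Meier estimate already planned.

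The cost is a few sentences in two documents. The sponsor gives up a ground it has no criterion to apply, and keeps the eCRF and the sites open for up to 12 months after an enrolment stop. No extra tests are needed, because section 9 already confines data collection to routine practice.

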#### 15.8.2. Early termination or suspension of the research site

The Sponsor, the EC of the site, or the regulating authority may decide to suspend or prematurely terminate a research site (due to, for example, cases of breach of the Clinical Investigation Plan or insufficient subject enrollment). If the investigational site is terminated prematurely or suspended, the Sponsor will inform the clinical investigators of the termination or suspension of the study and the reasons for this decision. If the site was evaluated by its own EC, the study closeout at the site must be reported, as well as the reference EC that evaluated it initially, and the study subjects at that research site or their legal representatives.

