# 8. Subject selection

# 8.1. Study population

The sample size will be approximately 1000 subjects who must be enrolled over the two-year period, based on the annual rate of cryoballoon ablations carried out in Spain.

All local and regional regulatory requirements must be met before the activation of each site and before the enrollment of subjects in the study. Each participating site should have the official confirmation from the sponsor authorizing them to start any study activity. Enrollment will last for 2 years. It is expected to commence in May 2016 and finish in May 2018.

A subject will be considered to be enrolled in the observational study from the moment in which he/she signs the Data Release Form for the study.

The investigator will keep a register of all the subjects enrolled in the study, linking each subject to a specific identification code for that site and that subject. This code will be assigned automatically by the electronic Case Report Form and will not contain any of the subject's personal information, so that the anonymity of the participating subjects is assured.

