## 9.2. Investigation Site Selection

An investigation site may be included in the observational study if the site meets the following requirements:

- > The site has demonstrable experience of the technique (at least 10 procedures a year),
- > The site has adequate resources, facilities, equipment and support staff
- > The site is capable of complying with the requirements of the registry, laws and local regulations, as well as Medtronic's requirements

According to local requirements a Clinical Trial Agreement or Investigator agreement will be in place depending on site specifics.

In order to document investigator experience and qualification a current (within 2 years) CV from the investigators will be collected

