## 9.9. Subject withdrawal or discontinuation

The study investigators can decide to remove the subject from the study in the following situations:

- Loss to follow-up over the course of the study. A patient will be considered as lost to follow after 3 attempts have been done to contact the patient without success and those are appropriately documented in the source documents
- Does not meet inclusion/exclusion criteria.
- The investigator thinks that it would be advisable for the subject to leave the study.

On the other hand, the subject has the right to terminate his/her participation in the study at any time during the course of the study.

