### **Treatment of missing values**

The statistical analysis process assumes the correct monitoring of the data entry through the electronic data collection notebook. During the data analysis phase, no queries should be made to fill in missing information or missing values.

However, during the analysis process, missing and missing values will be identified for later treatment with the research team. Extreme and out-of-range values will also be identified for later review by the research team. The necessary corrections obtained from the identification of out-of-range values or missing information and reviewed by the patient's clinical manager will be entered into the database for subsequent treatment in subsequent re-analyses.

The initial data treatment strategy will be to assume a non-response as a completely random missing value (MCAR) and the treatment of missing values will be isolated by variable. If it is required to relate several variables in an analysis, the treatment will be "according to the pair" of variables considered (pairwise) to minimize the impact of the lost information on the estimates obtained.

In the cases in which the analysis of several consecutive measurements is carried out or the passage of time is valued, the carrying over of the last value obtained on subsequent measurements will be assumed. For example, if a subject has not suffered an event or there is no information on this aspect (missing value) at the time of closing the database, it will be assumed that the subject's status is the same as the last measurement with valid data.

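### Section 15.8.2 lets a site be closed for low enrolment without keeping 12-month data collection open for subjects already ablated, and the SAP's carry-forward rule could then count them as AF-free

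*Protocol*

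**What the plan says.** **Site closure.** Protocol section 15.8.2 allows a site to be suspended, or allows the named bodies to "prematurely terminate a research site (due to, for example, cases of breach of the Clinical Investigation Plan or insufficient subject enrollment"). The rest of the section says who must be informed. Where the site's own ethics committee evaluated the study, "the study closeout at the site must be reported". No threshold for insufficient enrolment is given, and nothing is said about data collection on subjects already enrolled.

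**Follow-up.** Section 13.1 plans "a follow-up period of one year from the time of enrollment of each subject". Section 9.1 has one annual follow-up (±28 days), and Table 1 has a single follow-up column. The SAP's Follow-up section notes that it is not yet known whether a patient can have several visits. Section 9.9 lists the grounds on which investigators may remove a subject, and site closure is not among them.

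**Analysis.** Under Statistical models, the SAP reports the number and percentage without AF recurrence at 12 months, using the Follow-up and Adverse Event tables. It defines no denominator. Its section on missing values has two rules. The default assumes data missing completely at random, handled variable by variable. For consecutive measurements or the passage of time, the last value is carried forward; for a subject without an event or without information at database closing, "it will be assumed that the subject's status is the same as the last measurement with valid data".

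**The concern.** Low enrolment is a reason to stop recruiting at a site. It is not a reason to lose outcomes on subjects already treated there, since follow-up involves no tests beyond routine care (section 9). Section 15.8.2 treats the two as one act. A site closed before a subject reaches month 12 may take that subject's only scheduled primary assessment with it, along with later adverse event reports.

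The SAP example of a subject with no information at database closing describes this subject. Carried forward, the absence of a recorded recurrence becomes a success. The error runs in one direction, and it needs no difference in outcome between closed and open sites.

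**Working it through.** **Inputs from the documents.** N of about 1000 ("It is expected to include approximately 1000 subjects enrolled at approximately 30 Spanish sites"). This figure is set by feasibility ("based on the annual rate of cryoballoon ablations carried out in Spain"), with no precision, power or dropout input, so there is no derivation to reproduce.

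**Assumed inputs.** AF-free proportion p = 75% at every site; L = 50 or 15 subjects at closed sites with the 12-month assessment lost. For example, L = 50 is five sites of 10 subjects and L = 15 is three sites of 5. Neither document gives these values.

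**Carry-forward.** If all L subjects are counted as AF-free, the reported proportion is ((N − L)p + L)/N. The truth is p, so the bias is L(1 − p)/N.

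- L = 50: (950 × 0.75 + 50)/1000 = 76.25%, a bias of 50 × 0.25/1000 = +1.25 points.
- L = 15: (985 × 0.75 + 15)/1000 = 75.375%, a bias of 15 × 0.25/1000 = +0.375, about +0.4 points.

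For the given p and L these are upper limits, because they suppose that none of the lost subjects' recurrences was recorded before closure. If half had been, L = 50 would give 1.25 × 0.5 = about 0.6 points.

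**Sensitivity to p, with L = 50.** p = 60%: 50 × 0.40/1000 = 2.0 points. p = 70%: 50 × 0.30/1000 = 1.5. p = 80%: 50 × 0.20/1000 = 1.0.

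**Yardstick.** The 95% half-width at p = 75% is 1.96 × √(0.75 × 0.25/1000) = 2.7 points. Under carry-forward the bias equals this when L = 0.0268 × 1000/0.25 = 107, or roughly 11 sites of 10 subjects out of about 30.

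**Default rule instead.** If the L subjects leave the denominator and sites do not differ, the estimate stays at p. The only cost is precision: with 950 subjects the half-width is 1.96 × √(0.75 × 0.25/950) = 2.75 points against 2.68.

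**The case against.** The strongest reply is that section 15.8.2 is silent and does not say that follow-up ends. Section 13.1 plans a year for every subject, and the list opening "The study investigators can decide to remove the subject from the study in the following situations" does not include site closure. The closeout sentence is conditional and concerns notification. Section 15.1 is not in the text available for this review, and the site agreements foreseen in section 9.2 are separate documents, so any statement that nothing protects follow-up applies only to the visible text. All of this stands, and it is why the outcome *may* be lost rather than *will* be. It does not settle the matter: the general plan in 13.1 is not carried into the specific provision on closure.

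It can also be said that the upward bias comes from the carry-forward rule, which acts on missing status from any cause. That is true. Site closure is one avoidable source of such missing status.

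A reader might go further and infer that low-volume sites are selected out of the primary percentage. The entry criterion is "The site has demonstrable experience of the technique (at least 10 procedures a year"), so a site at that floor can supply at most 10 × 2 = 20 subjects in two years, against an average of 1000/30 = 33.3. The documents do not support this reading:

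- The 33.3 is the mean of two approximate planning figures, not a quota. Nothing says that a site enrolling 20 would be closed.
- Low enrolment is not low procedure volume. Section 6 expects every eligible subject to be enrolled, so a busy site may simply be under-enrolling.
- Neither document links enrolment or volume to recurrence, so the direction of any exclusion bias is unknown. Assuming 60% AF-free at closed sites and 75% elsewhere, with L = 50, the truth is (950 × 0.75 + 50 × 0.60)/1000 = 74.25%. Dropping the 50 gives 75.0% (+0.75 points) and carrying them forward gives 76.25% (+2.0). The 15-point gap has no source in the plan.
- Under carry-forward these subjects stay in the percentage, which is the opposite of being selected out.

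**Conclusion.** The point holds as a gap with a definite consequence, and it is minor. Closure for insufficient enrolment is expressly allowed, the visible text does not keep data collection open for subjects already ablated, and the SAP's carry-forward rule would count those without a recorded recurrence as AF-free. The SAP does not say whether that rule or the default missing-at-random rule governs the primary percentage. Under the default rule there is no bias unless sites differ.

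With 75% AF-free everywhere, the upward bias is at most about 1.25 points for 50 lost outcomes and about 0.4 points for 15, both inside the 2.7-point half-width. Sites closed for low enrolment bring few subjects by definition, so the effect stays small unless many close. Unlike sampling error, however, it is one-sided, and for a given share of lost subjects it does not shrink as N grows. Selection against low-volume sites is not established.

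**What to change.** 1. In section 15.8.2, state that insufficient enrolment closes a site to new enrolment only. The 12-month (±28 days) data collection and adverse event reporting continue for subjects already enrolled.
2. For closures on other grounds, report the number of sites and subjects affected.
3. In the SAP, treat unobserved 12-month status at closed sites as unknown, not AF-free, in the primary percentage, and state the denominator. Censor these subjects at last contact in the Kaplan-Meier analysis.

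The cost is a sentence or two in each document. In operation, eCRF access and remote review stay open at low-enrolling sites for up to about 13 months after the last ablation there (12 months plus 28 days). No additional tests are needed and the sample size does not change.
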